#### 6.4.2. Study Drug Administration

Patisiran will be administered under the supervision of the site personnel every 21 ( $\pm$ 3) days.

On all dosing days, patisiran will be administered as a 70-minute IV infusion (approximately 1 mL/minute for the first 15 minutes followed by approximately 3 mL/minute for the remainder of the infusion).

- If the patient experiences an IRR the infusion time may be extended up to 3 hours in the event of a mild or moderate IRR.
  - 1) If the patient experiences a mild or moderate IRR that resolves by slowing the infusion rate then no further premedication changes are recommended.
  - 2) If the patient experiences a severe IRR, then patisiran administration will not be resumed until the case is discussed with the Medical Monitor (see Section 6.4.3).
- If the infusion time for a patient was already extended on the parent study due to an IRR, that modified infusion duration may be continued on this study for that particular patient. Returning the patient's infusion duration to 70 minutes will require a discussion with the Medical Monitor.
- For the first 3 infusions of patisiran on this study, the patient's infusion site should be assessed for signs of any localized reaction during the infusion and for 30 minutes after the end of the infusion, and the patient will remain at the clinical site for 1 hour following completion of dosing.

If a patient does not receive a dose of patisiran within the dosing window ( $\pm$ 3 days), the dose will be considered missed and not administered.

Additional details can be found in the patisiran Pharmacy Manual.

In addition to study treatment, patients will receive the recommended daily allowance of vitamin A in an oral supplement.

#### 6.4.3. Suggested Guidelines for Management of Infusion-Related Reactions

Criteria for categorizing IRRs are provided in [Appendix 3](#).

- In the event of an IRR, the infusion of patisiran may be stopped and the patient closely monitored until resolution of the reaction. Drugs that may be used to facilitate resolution and permit resumption of patisiran administration include, but are not limited to: paracetamol/acetaminophen (or equivalent), additional histamine H1/H2 receptor antagonists (eg, ranitidine), NSAIDs, adrenaline, supplemental oxygen, IV fluids, and/or corticosteroids.
- Following resolution of a mild or moderate IRR that required interruption of the patisiran infusion, resumption of administration may occur at the Investigator's discretion at a slower infusion rate (but not to exceed 3 hours) for that dose and for all subsequent doses of patisiran. If the infusion is delayed, the administration of the infusion should be completed no more than 6 hours from the initial start of the infusion.
- Patisiran administration will not be resumed for any patient following a severe IRR until the case is discussed with the Medical Monitor.

- If after consultation with the Medical Monitor it is agreed that an individual patient's steroid premedication will be increased then the following steps are **recommended**:
  - 1) If the IRR occurred while the patient received 10 mg intravenous dexamethasone or equivalent at least 60 minutes before the infusion and did not resolve with slowing of the infusion rate, then the patient should be increased by multiples of 5 mg intravenous dexamethasone or equivalent at least 60 minutes before the infusion and/or 5 mg oral dexamethasone or equivalent the night before the intravenous infusion.
  - 2) Increased dose of premedication steroids should NOT exceed the combination of 20 mg intravenous dexamethasone or equivalent on the day of infusion and 8 mg oral dexamethasone or equivalent taken the night before the infusion.
  - 3) If the IRR occurred while the patient received less than 10 mg intravenous dexamethasone or equivalent, then the patient should return to the prior dose of intravenous dexamethasone or equivalent that did not result in an IRR.

Patients will be instructed to call the Investigator if they experience symptoms such as fever, chills, myalgia, or nausea/vomiting after discharge from the site.

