### Appendix 3: Categorization of Infusion-Related Reactions

Signs and symptoms of an infusion-related reaction (IRR) usually develop during or shortly after drug infusion and generally resolve completely within 24 hours of completion of infusion.

Signs/symptoms may include: allergic reaction/hypersensitivity (including drug fever), arthralgia (joint pain), bronchospasm, cough, dizziness, dyspnea (shortness of breath), fatigue (asthenia, lethargy, malaise), headache, hypertension, hypotension, myalgia (muscle pain), nausea, pruritus/itching, rash/desquamation, rigors/chills, sweating (diaphoresis), tachycardia, urticaria (hives, welts, wheals), vomiting.

Categorization of IRRs is as follows:

Categorization	Description
Mild	Mild reaction: infusion may be continued; if intervention is indicated it is minimal and additional treatment (other than paracetamol for delayed reactions) is not required.
Moderate	Moderate reaction: requires treatment including more intensive therapy (eg, IV fluids, nonsteroidal anti-inflammatory drug [NSAIDs]) in addition to infusion interruption but responds promptly to medication. Treatment is indicated for $\leq 24$ hours.
Severe	More than moderate reaction: not rapidly responsive to medication or to interruption of infusion; and/ or prolonged (treatment is indicated for $>24$ hours); recurrence of severe symptoms following initial improvement.

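### The Medical Monitor hold after an infusion reaction depends on a severity grade that takes no account of danger to life

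*Protocol*

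**What the plan says.** The hold appears twice in Version 3.1 Brazil. Section 6.4.3 states: "Patisiran administration will not be resumed for any patient following a severe IRR until the case is discussed with the Medical Monitor". Section 6.4.2 says that if a patient has a severe IRR, "then patisiran administration will not be resumed until the case is discussed with the Medical Monitor". Section 6.4.3 names Appendix 3 as the source of the grading criteria.

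Appendix 3 has three grades and none above Severe.

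- **Moderate** covers a reaction that needs more intensive therapy, with intravenous fluids and NSAIDs as examples, "in addition to infusion interruption but responds promptly to medication", and for which treatment is indicated for 24 hours or less.
- **Severe** reads "More than moderate reaction: not rapidly responsive to medication or to interruption of infusion", and/or treatment for more than 24 hours, or "recurrence of severe symptoms following initial improvement".

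After a mild or moderate IRR that interrupted the infusion and has resolved, "resumption of administration may occur at the Investigator's discretion at a slower infusion rate". This applies to that same dose. A delayed infusion should be finished within 6 hours of its first start.

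**The concern.** The hold exists so that a second physician considers the case before the patient is exposed again. It is triggered by a grade that measures how quickly a reaction is controlled and how long treatment lasts. It does not measure how dangerous the reaction was. Appendix 3 counts hypersensitivity, bronchospasm and hypotension among the signs of an IRR. Such a reaction can put a patient in danger of dying and still reverse soon after treatment.

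Two investigators who both follow the text could handle the same event differently. One grades it severe, stops dosing and calls the Medical Monitor. The other grades it moderate and restarts the infusion that day. The harm at stake is death or serious injury on re-exposure. Section 1.3 confirms that patients who were on placebo in the parent study enter this one, so for them these are the first patisiran infusions.

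**Working it through.** No statistical figure is involved. The check applies the protocol's own criteria to a test case and then looks for any other clause that would close the gap.

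**Test case.** A patient develops bronchospasm and hypotension during the infusion and is in immediate danger. The infusion is stopped, the patient responds promptly to treatment, treatment is needed for less than 24 hours, and nothing recurs.

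| Appendix 3 criterion | Test case | Met? |
|---|---|---|
| Severe 1: slow to respond to medication or interruption | Responds promptly | No |
| Severe 2: treatment indicated for more than 24 hours | Less than 24 hours | No |
| Severe 3: recurrence of severe symptoms | None | No |
| Moderate: intensive therapy plus interruption, prompt response, 24 hours or less | All present | Yes |

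Listed Severe criteria that refer to danger to life: 0 of 3. The therapies named under Moderate are examples, so stronger treatment does not by itself move the event out of that row.

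**Rescue drugs.** Section 6.4.3 says: "Drugs that may be used to facilitate resolution and permit resumption of patisiran administration include, but are not limited to" several agents, among them "adrenaline, supplemental oxygen, IV fluids, and/or corticosteroids". The list covers IRRs of any grade, so it does not settle the grade. It does show that needing adrenaline or oxygen is not in itself a trigger for the hold.

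**Other clauses that might act as a hold.**

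| Section | What it requires | Holds a dose because of an IRR? |
|---|---|---|
| 3.1 | Medical Monitor consulted on exceptions to Day 0 timing | No |
| 3.1, 6.4.2 | Medical Monitor discussion before an extended infusion returns to 70 minutes | No |
| 6.4.1, 6.4.3 | Medical Monitor consulted if premedication is changed | No, only if a change is wanted |
| 4.3, 5.3 | Medical Monitor involved after 3 consecutive missed doses | No |
| 4.3 | Sponsor consulted after a serious or intolerable event, before the patient is discontinued | No, it governs stopping, not continuing |
| 9.2.1.2 | Defines life-threatening as a seriousness criterion | No, the consequence is a report |
| 9.5.1 | Serious event reported to the CRO immediately and always within 24 hours; treated by the Investigator's best judgment | No, the report is not a condition for re-dosing |

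On timing, a resumed infusion should end within 6 hours of its first start, while the outer limit for the report is 24 hours from awareness. Even a report made at once would not bar the restart, because the two are not linked.

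**Other versions.** The Brazil 2.1 and the France and Germany 2.1 versions carry the same hold and the same table. The Argentina 3.1 version has the same Appendix 3; its Section 6.4.3 is not in the part examined.

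**The case against.** The strongest reply is that the Severe row opens by calling the reaction more than moderate, and an event that nearly kills a patient is more than moderate in ordinary language. The count of 0 of 3 leaves that lead-in out. The Moderate examples also suggest a milder picture. Section 9.4 separately requires adverse events to be graded, with severe meaning incapacitating, and it would be odd to record an event as severe there and treat it as moderate for dosing.

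Further, Section 6.4.3 is headed as suggested guidance. Resumption is permitted rather than directed, follows resolution, and is at a slower rate. By the next dose, about 21 days later, the serious event will have been reported. The Pharmacy Manual and the Investigator's Brochure, both cited for further detail, are not available here and may say more. The proposed clause still relies on the investigator's judgment.

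Much of this stands as mitigation. The lead-in and Section 9.4 do allow a grade of severe, and many investigators would choose it. Neither compels it, because the text after the colon spells out what severe means and Section 6.4.3 names Appendix 3, not Section 9.4, for IRRs. Despite the heading, the hold is worded as a prohibition and is repeated in Section 6.4.2. Reporting before the next dose does not reach the same-day restart. As for judgment, the investigator must already decide whether an event is life-threatening in order to report it as serious. The clause uses that decision directly and removes the uncertain step of translating it into an Appendix 3 grade.

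**Conclusion.** The concern holds. As written, a life-threatening IRR that responds promptly can be graded moderate and the infusion resumed the same day without discussion with the Medical Monitor. The protocol already treats the Investigator's judgment alone as insufficient after a severe IRR, and speed of response is a weak reason to leave out reactions that endangered life.

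The gap is narrow. It covers only IRRs that are life-threatening, respond promptly and need treatment for 24 hours or less. The documents do not say how many to expect; the number is probably small, and patisiran is described as generally well tolerated in the earlier studies. Premedication, site supervision, the slower rate and one hour on site after each of the first 3 infusions lower the risk, but none of them requires a second opinion before re-exposure. The conclusion rests on the Version 3.1 Brazil text and assumes that the Pharmacy Manual and the Investigator's Brochure add no such hold. The change should be made; it does not affect the validity of any analysis.

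**What to change.** Leave the Appendix 3 scale as it is, so that IRR grades stay comparable with those already recorded. In the hold sentence of both Section 6.4.2 and Section 6.4.3, insert after the words for a severe IRR: *or any IRR that is life-threatening (Section 9.2.1.2), regardless of speed of response,*. Because the hold is an outright prohibition and the resumption rule is only permissive, the extended hold takes precedence over the Investigator's discretion for these events. Make the same insertion in every protocol version that carries the sentence.

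The cost is one clause in two sections, using the existing Medical Monitor and a term the protocol already defines. There will be a few more calls, and now and then a dose will be missed or left incomplete because the discussion cannot be finished in time. Section 5.3 already accepts occasional missed doses.

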### **6.5. Study Drug Accountability**

The Investigator or designee will maintain accurate records of receipt and the condition of the patisiran supplied for this study, including dates of receipt. In addition, accurate records will be kept of the weight used to calculate each dispensed patisiran dose, and when and how much patisiran is dispensed and used by each patient in the study. Any reasons for departure from the protocol dispensing regimen must also be recorded.

Drug accountability records and inventory will be available for verification by the Sponsor or designee.

Further instructions about drug accountability are detailed in the patisiran Pharmacy Manual.

### **6.6. Study Drug Handling and Disposal**

All used, partially used, and unused vials of patisiran will be returned to the Sponsor or its specified designee/depot or destroyed at the site according to applicable regulations.

Patisiran supplied for this study must not be used for any purpose other than the present study. Drug that has been dispensed for a patient and returned unused must not be redispensed.

## **7. PHARMACOKINETIC ASSESSMENTS**

No PK assessments will be performed in this study.

## 8. ASSESSMENT OF EFFICACY

### 8.1. Efficacy Parameters

Efficacy assessments may be performed at Day 0 if not performed during the parent study within 45 days of the first dose in this study. Efficacy assessments will occur for all patients at the 52-week visit, which will take place at the CAS. Patients will not receive study drug at this visit. A subset of the efficacy assessments performed at 52 weeks will be performed annually thereafter. The specific timing for each assessment is presented in [Table 1](#).

For the 52-week time point, a central neurologic testing core facility will review the data derived from the various neuropathy measures at each participating site to ensure compliance with testing procedures and quality of the data. A central echocardiography core lab will analyze the echocardiogram data. A core lab will be responsible for processing and analyzing skin punch biopsy samples.

Further details on performing the efficacy assessments will be provided in the Study Reference Manual.

#### 8.1.1. Neurological Testing

Neurological testing will be performed and the results of these tests will be used to calculate the Neuropathy Impairment Score (NIS), modified NIS (mNIS+7), and NIS+7, at the time points specified in [Table 1](#).

##### 8.1.1.1. Modified Neurological Impairment Score +7 and Neurological Impairment Score +7

The mNIS+7 assessment tool is a composite measure of neurologic impairment which includes the following measures:

- Clinical exam-based NIS (weakness and reflexes)
- Electrophysiologic measures of small and large nerve fiber function (+7) including:
  - Nerve conduction studies (NCS) 5 attributes ( $\Sigma 5$ )
  - Quantitative sensory testing (QST) by body surface area including touch pressure (TP) and heat pain (HP)
- Autonomic function (postural blood pressure)

Neurologic impairment will also be assessed by NIS+7. The NIS+7 consists of the following measures:

- Full NIS (including weakness, sensation, and reflexes)
- Electrophysiologic measures of small and large nerve fiber function (+7) including:
  - NCS  $\Sigma 5$
  - Vibration detection threshold (VDT)
- Heart rate response to deep breathing (HRdb)

The scoring and components of the mNIS+7 and NIS+7 are summarized in [Appendix 4](#). Components that are shared between the mNIS+7 and NIS+7 (including NIS and NCS) will be performed once at each assessment.

Every effort will be made to use the same devices for NCS, QST, and VDT for a patient throughout the duration of the study.

For each patient, 2 independent assessments of the mNIS+7 and NIS+7 will be performed at each time point at a CAS. Assessments are to be performed at least 24 hours (approximately) apart from each other but no greater than 7 days apart. In order to limit potential intra-operator bias, results of any of the prior assessments will not be available to the examiner when performing the second assessment. Each site will make every effort to have these assessments at the Week 52 visit performed by the same study personnel who performed the assessments for the patient in the patisiran study in which they were previously enrolled. Assessments of the NIS during the annual visit (after the Week 52 visit) must be performed by a neurologist.

#### **8.1.1.2. Neurological Impairment Score**

At each time point when only the full NIS is required, 1 assessment of the NIS will be performed at a CAS or PCS.

#### **8.1.2. Familial Amyloidotic Polyneuropathy Stage and Polyneuropathy Disability Score**

Changes in ambulation will be evaluated through the polyneuropathy disability (PND) score and FAP stage (see [Appendix 5](#) and [Appendix 6](#), respectively).

#### **8.1.3. Intraepidermal Nerve Fiber Density and Sweat Gland Nerve Fiber Density**

Quantification of nerve fibers in skin will be assessed via intraepidermal nerve fiber density (IENFD) and sweat gland nerve fiber density (SGNFD). For patients who had skin biopsies on the parent study and who have provided additional voluntary consent for skin biopsy on this study, 2 sets of tandem 3-mm skin punch biopsies (4 biopsies total) for IENFD and SGNFD will be obtained at each time point. One set of biopsies will be taken from the distal lower leg, when a patient's clinical status allows, and 1 set from the distal thigh.

Details on sample collection, processing, and storage will be provided in the Study Laboratory Manual.

Skin biopsies will be performed at a CAS or PCS.

#### **8.1.4. Modified Body Mass Index**

Sites will measure body weight on all dosing days. Using that data, the modified body mass index (mBMI) will be calculated ( $BMI \times \text{albumin}$ ) programmatically in the clinical database and does not need to be performed at the study center.

#### **8.1.5. Timed 10-meter Walk Test**

To perform the timed 10-meter walk test, the patient will be asked to walk 10 meters. The walk must be completed without assistance from another person; ambulatory aids such as canes and walkers are permitted. The time required for the patient to walk 10 meters will be recorded.

Two assessments of the 10-meter walk test are to be conducted on separate days (1 assessment on each day). The second (repeat) assessment must be conducted at least 24 hours (approximately) but not more than 7 days after the first assessment. Each site will make every effort to have this assessment performed by the same Investigator.

#### **8.1.6. Grip Strength Test**

Hand grip strength is to be measured by dynamometer. Sites will be trained on dynamometer and testing for the study. When performing the test, patients will stand, holding the dynamometer in their dominant hand, with their arm parallel to the body without squeezing the arm against the body. Tests will be performed in triplicate for each assessment. Two assessments of the grip strength test are to be conducted on separate days (1 assessment on each day). The second (repeat) assessment must be conducted at least 24 hours (approximately) but not more than 7 days after the first assessment.

Every effort will be made to use the same dynamometer for a patient on both assessment days.

#### **8.1.7. Composite Autonomic Symptom Score**

To evaluate changes in autonomic symptoms, patients will complete the Composite Autonomic Symptom Score (COMPASS 31) questionnaire. The questionnaire consists of 31 clinically selected questions evaluating 6 autonomic domains (orthostatic intolerance, secretomotor, gastrointestinal, bladder, and pupillomotor).

#### **8.1.8. Norfolk Quality of Life - Diabetic Neuropathy Questionnaire**

Quality of life will be assessed through the Norfolk Quality of Life - Diabetic Neuropathy (QOL-DN) questionnaire, a standardized 47-item patient-reported outcomes measure that is sensitive to the different features of diabetic neuropathy (DN)-small fiber, large fiber, and autonomic nerve function.

Patients who are entering this study from a protocol that does not include the Norfolk QOL-DN questionnaire (eg, ALN-TTR02-003) will not complete this assessment.

#### **8.1.9. EuroQoL Quality of Life Questionnaire**

Quality of life will also be assessed through the use of the EuroQOL (EQ-5D) questionnaire, a standardized 5 question instrument for use as a measure of health outcomes.

#### **8.1.10. Rasch-built Overall Disability Scale**

An assessment of the disability each patient experiences will be assessed through the Rasch-built Overall Disability Scale (R-ODS). The R-ODS consists of a 24-item linearly weighted scale that specifically captures activity and social participation limitations in patients.

#### **8.1.11. Pharmacoeconomics Questionnaire**

The burden of disease and healthcare utilization will be assessed using a patient-reported pharmacoeconomics questionnaire. This assessment will be performed at the location of the patient's scheduled visit.

### **8.1.12. Echocardiogram and Biomarkers of Cardiac Function**

Cardiac structure and function will be assessed through echocardiograms and measurement of serum levels of the cardiac biomarkers N-terminal prohormone of B-type natriuretic peptide (NT-proBNP) and troponin I.

Echocardiograms will be performed and interpreted at a central echocardiography core laboratory. Patients entering this study from Study ALN-TTR02-003 who were not previously participating in the cardiac subgroup study will also be required to have an echocardiogram performed before dosing on Day 0. Image acquisition, storage, and transfer guidelines will be provided in a Study Manual.

Blood samples will be drawn to measure levels of NT-proBNP and troponin I. Details on sample collection, processing, and storage will be provided in a Study Laboratory Manual.

